#### **10.2 Risk Minimization**

Refer to "Prevention and Mitigation" column in the table under **Section 10.1**.

#### **10.3 Potential Benefits**

The main benefit of this study is that subjects may experience improved glucose control. They may gain increased awareness of emerging technologies for diabetes management as a result of their participation.

#### **10.4 Risk-Benefit Rationale**

The main benefit of this study is that subjects may experience improved glucose control. With all closed loop insulin pumps, there is a risk that the pump will deliver too much or not enough insulin, resulting in hypoglycemia or hyperglycemia. These risks have been minimized through previous characterization of the performance of the DS5 and a variety of safety checks that are an integral part of the MiniMed 780G closed loop algorithm.

#### **10.5 Risk Determination**

In the opinion of the sponsor, this study is considered to be a significant risk (SR) study. Results of an

evaluation of the requirements per 21 CFR Part 812.3, led to the SR determination as follows:

- The devices present potential for serious risk to subject health, safety, or welfare.
- The devices are for a use of substantial importance in treating disease, and presents potential for serious risk to subject health, safety, or welfare.

Therefore, submission of an Investigational Device Exemption (IDE) application to the United States FDA is required.

### **11. Adverse Events**

#### **11.1 Adverse Events**

Throughout the course of the study, investigational centers will make all efforts to remain alert to possible reportable adverse events (AEs) or untoward findings. The study personnel will elicit reports of

CIP337 Clinical I	nvestigation Plan		
D00459337	Version A	Page 65 of 97	Medtronic

AEs from the subject at each visit (including phone calls) starting at the time of signing the informed consent documenting the medical diagnosis, date of event start and end, causality (relationship to device or procedure), treatment, outcome, assessment of seriousness, and description that includes the details of the event.

#### **11.2 Definitions and Classification of Adverse Events**

Medtronic uses the definitions provided in ISO 14155:2020 and 21 CFR 812 for AE definitions. Where the definition indicates "device", it refers to any device used in the study. This might be the device under investigation, or any market released component of the system.

**Severe Hypoglycemia** is an event requiring assistance of another person due to altered consciousness to actively administer carbohydrate, glucagon, or other resuscitative actions.

This means that the subject was impaired cognitively to the point that he/she was unable to treat himself or herself, was unable to verbalize his or her needs, and was incoherent, disoriented and/or combative.

These episodes may be associated with sufficient neuroglycopenia to induce seizure or coma. Plasma glucose measurements may not be available during such an event, but neurological recovery attributable to the restoration of plasma glucose to normal is considered sufficient evidence that the event was induced by a low plasma glucose concentration.

**Severe Hyperglycemia** is defined as hyperglycemia (BG greater than [>] 300 mg/dL or 16.7 mmol/L) with BG ketones greater than (>) 1.5 mmol/L, and/or accompanied by symptoms of nausea, vomiting or abdominal pain.

The meter and ketone test strips are supplied for the evaluation of ketone monitoring. Only blood ketones will be recognized (not urine ketones) for assisting in diagnosis of severe hyperglycemia. The monitors/test strips are quality controlled prior to dispensing to subjects. Blood ketones provide contemporaneous understanding of ketone levels associated with elevations in glucose.

**Diabetic Ketoacidosis/DKA diagnostic criteria**: BG greater than (>) 250 mg/dL or greater than (>) 13.9 mmol/L, arterial pH less than (<) 7.3, bicarbonate less than (<) 15 mEq/L, moderate ketonuria or ketonemia and requiring treatment within a health care facility. 

Hyperglycemic events will be recorded as DKA if the event includes the presence of all of the following:

- Arterial blood pH less than (<) 7.30 or serum bicarbonate less than (<) 15 mEq/L
- Blood glucose greater than (>) 250 mg/dL or greater than (>) 13.9 mmol/L
- Serum ketones or large/moderate urine ketones
- Symptoms such as polyuria, polydipsia, nausea, or vomiting
- Treatment provided in a health care facility

D00459337

#### Adverse Event (AE) (ISO 14155:2020)

Untoward medical occurrence, unintended disease or injury, or untoward clinical signs (including abnormal laboratory findings) in subjects, users or other persons, whether or not related to the investigational medical device and whether anticipated or unanticipated.

**Note 1 to entry:** This definition includes events related to the investigational medical device or the comparator.

**Note 2 to entry:** This definition includes events related to the procedures involved.

**Note 3 to entry:** For users or other persons, this definition is restricted to events related to the use of investigational medical devices or comparators.

#### Adverse Device Effect (ADE) (ISO 14155:2020)

Adverse event related to the use of an investigational medical device.

**Note 1 to entry:** This definition includes adverse events resulting from insufficient or inadequate instructions for use, deployment, implantation, installation, or operation, or any malfunction of the investigational medical device.

**Note 2 to entry:** This definition includes any event resulting from use error or from intentional misuse of the investigational medical device.

**Note 3 to entry:** This includes 'comparator' if the comparator is a medical device

#### Serious Adverse Event (SAE) (ISO 14155:2020)

Adverse event that led to any of the following

- a) death,
- b) serious deterioration in the health of the subject, users, or other persons as defined by one or more of the following:
  - 1. a life-threatening illness or injury, or
  - 2. a permanent impairment of a body structure or a body function including chronic diseases, or
  - 3. in-patient or prolonged hospitalization, or

- 4. medical or surgical intervention to prevent life-threatening illness or injury or permanent impairment to a body structure or a body function,
- c) foetal distress, foetal death or a congenital abnormality or birth defect including physical or mental impairment

**Note 1 to entry:** Planned hospitalization for a pre-existing condition, or a procedure required by the CIP, without serious deterioration in health, is not considered a serious adverse event.

#### Serious Adverse Device Effect (SADE) (ISO 14155:2020)

Adverse device effect that has resulted in any of the consequences characteristic of a serious adverse event

#### Unanticipated Adverse Device Effect (UADE) (21 CFR 812.3(s))

Any serious adverse effect on health or safety or any life-threatening problem or death caused by, or associated with, a device, if that effect, problem, or death was not previously identified in nature, severity, or degree of incidence in the investigational plan or application (including a supplementary plan or application), or any other unanticipated serious problem associated with a device that relates to the rights, safety, or welfare of subjects.

#### **11.3 Recording of Adverse Events**

The investigator or designee will record ALL AEs while the subject is enrolled in the clinical study.

Each AE needs to be assessed for its device or procedure relatedness. A device related AE is associated with the use of the study device (e.g., infection of sensor site or infusion set occlusion resulting in DKA). A procedure related AE is associated with testing related to the study procedures specified in the CIP (e.g., needle (blood draw) insertion pain).

Examples of device or procedure related AEs include:

- **Device** related (ADE): insertion site infection
- Serious adverse *device effect*: cellulitis at device insertion site requiring hospitalization
- Procedure related AE: bruising at needle (blood draw) insertion site

Subjects participating in the study have diabetes and are expected to experience hypoglycemia and or hyperglycemia. These normal events are not expected to be reported to sponsor as this is not considered an untoward event, but rather an expected occurrence. Any glycemic excursion that meets the CIP definition of severe hypoglycemia, severe hyperglycemia or DKA is considered an untoward event and a worsening from the subject's baseline and would be reported to sponsor on an AE eCRF.

CIP337 Clinical	Investigation Plan		
D00459337	Version A	Page 68 of 97	Medtronic

Baseline medical conditions should only be reported to sponsor on an AE eCRF if there is a worsening from the subject's baseline. For example, a subject previously diagnosed with asthma is hospitalized for severe asthma attack would be a reportable event.

Adverse events will be documented in the subject source file and reported to sponsor on an eCRF. The investigational center is responsible for documentation of AEs including obtaining source documents related to the event, such as emergency medical technician/paramedic reports, hospital records (admission summary; lab results, test results, discharge summary) or device uploads to support the event. Source documents will be reviewed to determine if additional AEs have occurred and require reporting.

Adverse events that have not resolved at the time of the subject's discontinuation or completion of the study should have an "outcome" of Not Recovered/Not Resolved at study end in subject source and on an eCRF. The investigator should ensure that subject is aware of any follow-up or additional treatment that is required for any ongoing AE at EOS participation; however, there will be no eCRF entry for the ongoing follow-up.

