- During the course of the study, subject is taking oral, injectable, or IV glucocorticoids
- During the study, (female) subject becomes pregnant.
- During the study, the subject experiences one severe hypoglycemic episode, if it is related to the use of MiniMed 780G system SmartGuard feature.
- During the study, the subject experiences one episode of DKA, if it is related to the use of MiniMed 780G system SmartGuard feature.
- During the study, subject has a cardiovascular event or any vascular event such as stroke.

Documentation of the reason(s) leading to subject withdrawal will be kept in the subject's source documentation.

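### Adverse events still open at exit, including serious ones that themselves force withdrawal, are closed as unresolved, with no eCRF capture of the later outcome

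*Protocol*

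**What the plan says.** Protocol section 11.3 sets the recording window: "The investigator or designee will record ALL AEs while the subject is enrolled in the clinical study". It then deals with events that are open when participation ends. "Adverse events that have not resolved at the time of the subject's discontinuation or completion of the study" are given the outcome Not Recovered/Not Resolved, both in source and on an eCRF. The investigator is to make sure the subject knows of any further treatment or follow-up needed; "however, there will be no eCRF entry for the ongoing follow-up". The rule covers all adverse events and does not single out serious ones.

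Section 11.1 lists what is collected for each event, including "date of event start and end, causality (relationship to device or procedure), treatment, outcome, assessment of seriousness".

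Section 9.8 lists the reasons for mandatory withdrawal. Three of them are themselves potentially serious adverse events:
- "During the study, subject has a cardiovascular event or any vascular event such as stroke", with no condition on relatedness;
- "During the study, the subject experiences one episode of DKA, if it is related to the use of MiniMed 780G system SmartGuard feature";
- a single severe hypoglycemia event, again only where SmartGuard use is implicated.

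Section 9.8 also requires withdrawal when the investigator judges that continuing would compromise health or safety. After exit, care passes to the subject's own providers.

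The SAE definition in section 11.2 counts death and "a permanent impairment of a body structure or a body function including chronic diseases" among its criteria.

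**The concern.** Closing the record at the end of participation is common and is usually harmless, because the cut-off has nothing to do with the event. Here, for some of the most serious event types, the event causes the exit and the exit closes the record. Whether the final outcome is captured therefore depends on the type of event.

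A stroke is the clearest case. Withdrawal is mandatory whatever the cause, and the lasting deficit may not be known when the subject leaves. The database would show an unresolved event with no end date, and a later death or permanent impairment would have no required place in it.

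Section 5.2 gives further confirmation of safety as the reason for the study. The outcome of serious events is part of that evidence.

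**Working it through.** The plan states no figure on this point, so the check is a comparison of sections.

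1. **Which events are caught.** The rule in 11.3 applies only to events unresolved at exit. An episode of severe hypoglycemia or DKA that resolves before exit keeps its true outcome and end date, both of which 11.1 collects.

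2. **Which events force exit.** Under 9.8, severe hypoglycemia and DKA do so only if related to SmartGuard. A cardiovascular or vascular event always does.

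3. **How long between event and exit.** Section 9.8 sets no interval. Exit involves some activity: the Exit eCRF and, after Visit 7, a final HbA1c (section 9.1), and device return (section 9.8). None of these holds the AE record open until the outcome is known.

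4. **Whether another section fills the gap.**
   - *Sections 11.3 and 11.4:* the site obtains hospital and discharge records to support the event and provides them on request. Neither section asks for the outcome after exit.
   - *Section 12.1:* the Clinical Events Committee (CEC) may delay its disposition until records arrive, and the CRF is updated if the investigator accepts its adjudication. That update concerns how the event is classified.
   - *Section 12.2:* the sponsor updates the FDA on UADEs and on device-related DKA and severe hypoglycemia. An unrelated stroke is not on that list, and an update to the agency is not a database entry.
   - *Sections 9.8, 12.2 and 16.10.2:* care after withdrawal or stopping is by the subject's own providers.

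   No section requires the post-exit outcome to be sought or entered.

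5. **Whether any planned analysis uses the outcome.** SAP 7.9.6 summarizes event types and incidence in windows ending at end of study or exit, and SAP 7.10 lists similar items. Neither lists AE outcome. The primary and secondary endpoints are HbA1c change, time in range and time below 54 mg/dL.

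6. **Whether a count can be derived.** With 200 subjects entering the study period and 90 days each, exposure is 200 × 90 / 365.25 = 49.3 patient-years. The rates in protocol Table 5 run from 0 to 20.9 per 100 patient-years for severe hypoglycemia and from 0 to 9.9 for DKA:
   - severe hypoglycemia: 49.3 × 20.9 / 100 = 10.3, so 0 to 10.3 events;
   - DKA: 49.3 × 9.9 / 100 = 4.9, so 0 to 4.9 events.

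   Using only the 530G in-home studies in that table, the highest rates are 1.42 and 3.4, giving 49.3 × 1.42 / 100 = 0.7 and 49.3 × 3.4 / 100 = 1.7. All of these count every event. The affected events must also be unresolved at exit and, to have forced the exit, related to SmartGuard. The documents give neither share, and Table 5 has no cardiovascular rate. The number affected cannot be computed.

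**The case against.** The strongest reply is that 11.3 is an explicit and internally consistent choice, that no planned estimate depends on AE outcome, and that an inpatient stroke or DKA is already serious whatever happens later. All of that stands. It limits the point to completeness of the record for a few events, and late changes in seriousness should be rare.

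Several stronger readings are tempting, and the documents do not support them.

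- *That every withdrawal-forcing event ends up coded as unresolved or is lost.* The code applies only to events open at exit, and source records may hold later information.
- *That the CEC's view of seriousness is fixed at exit.* Section 12.1 lets the committee wait for records, does not limit it to pre-exit data, and provides for a CRF update after adjudication.
- *That pregnancy is frozen by the same rule.* It is a reason for withdrawal in 9.8, but the protocol does not define pregnancy itself as an adverse event, so 11.3 does not govern it. Follow-up of pregnancies is a separate question.
- *That the Table 5 rates give the number affected.* They span very different populations, and section 12.2 itself notes that the registry rates exceed those in the clinical studies. They also precede the two filters in step 6.
- *That subjects are left without care.* Section 11.3 has the investigator tell the subject what follow-up is needed. What is missing is capture of the data.

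**Conclusion.** The point holds in a limited form. For adverse events unresolved at exit, including serious ones that themselves require withdrawal, the protocol fixes the outcome as Not Recovered/Not Resolved and rules out eCRF entry of what follows. The other safeguards cover this in part, and none requires the later outcome to be entered.

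The events affected are likely to be few, and their number is unknown. The endpoint tests, the pass/fail decision and the planned incidence summaries do not change. What would improve is the completeness of outcome, duration and late seriousness for serious events. This is an inexpensive improvement and does not bear on the validity of the main results.

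The conclusion assumes that no separate document, such as the eCRF completion instructions, requires post-exit outcomes to be entered. It takes no position on the withdrawal rules.

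**What to change.** Amend protocol section 11.3 so that any SAE, SADE, UADE, severe hypoglycemia or DKA still open at exit is followed, by phone or from records, until it has resolved, is stable, or a last contact date set by the sponsor is reached. Enter the final outcome, its date and any change in seriousness on the AE eCRF. Add to the SAP a listing of serious-event outcomes, since the tables in 7.9.6 do not show outcome. Keep the present rule for all other adverse events.

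The cost is a change of wording, a few contacts after exit, and some AE forms kept open slightly longer. An event that is outside these categories at exit and worsens later would still not be captured; that is the price of keeping the change small.

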#### **11.4 Notification of Adverse Events**

Sponsor Notification:

The investigational center staff must report all AEs to Medtronic in a timely manner. All severe hypoglycemia, DKA, SAE, SADE, and UADE should be reported as soon as possible (desired within 24 hours of investigator or study coordinator awareness) to Medtronic. For the previously mentioned events, the AE eCRF will be completed with all known details as soon as possible and this will serve as notification to Medtronic. If the study database cannot be accessed due to technical problems, contact the sponsor via email at [contact] and provide the de-identified known details of the event. Once the access issue has been corrected, the event should be entered onto an AE eCRF.

Source documents that support the event (e.g., clinic notes, hospital admission and discharge records, lab reports, EMT reports, ER/Urgent Care) should be provided upon request to the sponsor via Medtronic's secure upload application. All source documents/medical records should be redacted of patient identifiers (full name, address, etc.) prior to providing to the sponsor. Each source page should be identified with the subject ID.

#### **11.5 Expedited Safety Reporting Requirements**

For device studies, investigators are required to submit a report of a UADE to the sponsor and the reviewing IRB as soon as possible, but in no event later than 10 working days after the investigator first learns of the event (812.150(a)(1)). See **Section 12.2** for expedited reporting requirements for UADE.

CIP337 Clinical	Investigation Plan		
D00459337	Version A	Page 69 of 97	Medtronic

The sponsor will notify the investigator and IRB of any event that results in a safety report per regulations to the FDA. Documentation of IRB notification of any safety event must be kept at the investigational center and a copy sent to the sponsor.

#### It is the responsibility of the investigator to follow their IRB reporting requirements.

#### **11.6 Causality Assessment**

An AE is not automatically related to the study device or procedure simply because the subject is wearing the device and participating in the study. The event should be reviewed to determine if the device or study procedure could have possibly caused the event and therefore is related to the study device or procedure.

Causality assessment is the determination of the relationship between an AE and the device being studied. It is expected that the investigational center will review all elements surrounding the AE to properly assess the causality of the event to the study device or to a study procedure.

This review would include the subjects' description of the event, study device uploads and medical records (if applicable) from the treating facility. These records will be made available to sponsor.

Investigators should classify the relationship between the AE and the study device or study procedures using one of the four possible causality categories listed below:

- **Not related:** relationship to the device, comparator, or procedures can be excluded when:
  - the event has no temporal relationship with the use of the investigational device or the procedures related to the application of the investigational device;
  - the event does not follow a known response pattern to the medical device (if the response pattern is previously known) and is biologically implausible;
  - the discontinuation of medical device application or the reduction of the level of activation/exposure – when clinically feasible – and reintroduction of its use (or increase of the level of activation/exposure), do not impact on the event;
  - the event involves a body-site or an organ not expected to be affected by the device or procedure;
  - the event can be attributed to another cause (e.g., an underlying or concurrent illness/ clinical condition, an effect of another device, drug, treatment or other risk factors);
  - the event does not depend on a false result given by the investigational device used for diagnosis, when applicable;

In order to establish the non-relatedness, not all the criteria listed above might be met at the same time, depending on the type of device/procedures and the event.

• **Possible:** the relationship with the use of the investigational device, comparator, or the relationship with procedures, is weak but cannot be ruled out completely. Alternative causes are also possible (e.g., an underlying or concurrent illness/clinical condition or/and an effect of

## CIP337 Clinical Investigation Plan Page 70 of 97 Medtronic D00459337 Version A Page 70 of 97 Medtronic

another device, drug or treatment). Cases where relatedness cannot be assessed, or no information has been obtained should also be classified as possible.

- **Probable**: the relationship with the use of the investigational device, comparator, or the relationship with procedures, seems relevant and/or the event cannot reasonably be explained by another cause.
- **Causal relationship:** the event is associated with the investigational device, comparator, or with procedures beyond reasonable doubt when:
  - the event is a known side effect of the product category the device belongs to or of similar devices and procedures;
  - the event has a temporal relationship with investigational device use/application or procedures;
  - o the event involves a body-site or organ that
    - the investigational device or procedures are applied to;
    - the investigational device or procedures have an effect on;
  - the event follows a known response pattern to the medical device (if the response pattern is previously known);
  - the discontinuation of medical device application (or reduction of the level of activation/exposure) and reintroduction of its use (or increase of the level of activation/exposure), impact on the event (when clinically feasible);
  - other possible causes (e.g., an underlying or concurrent illness/clinical condition or/and an effect of another device, drug or treatment) have been adequately ruled out;
  - harm to the subject is due to error in use;
  - the event depends on a false result given by the investigational device used for diagnosis, when applicable;

In order to establish the relatedness, not all the criteria listed above might be met at the same time, depending on the type of device/procedures and the event.

